Open-Label Randomized Controlled Trial to Assess Preoperative Acupuncture for Patients Undergoing Total Knee or Hip Arthroplasty

OVERVIEW

Acupuncture has been extensively practiced and studied worldwide, particularly as a part of Eastern medicine, but it is a relatively uncommon therapy offered in Western medical institutions, such as those in the United States. Considering the commonly cited benefits of acupuncture, such as reduced anxiety and pain, hospitals throughout the United States have the opportunity to implement acupuncture as a cost-effective and safe technique for improving surgical outcomes.

Acupuncture administered in the preoperative period can be particularly effective for reducing preoperative anxiety, postoperative pain, postoperative opioid consumption, and postoperative nausea and vomiting. Consequently, preoperative acupuncture can improve patient satisfaction and decrease hospital costs. However, due to lack of implementation and experience, further research is needed to establish the safety and efficacy of preoperative acupuncture in the United States medical practices.

At the Bone-and-Joint Institute at Hartford Hospital, where this study is proposed, a quality study on total knee or hip arthroplasty patients found that 21% of its monthly patients were “high-anxiety” according to the Amsterdam Preoperative Anxiety and Information Scale (APAIS). Thus, there is a significant population of patients that would benefit from a procedure to reduce preoperative anxiety at our facility.

This proposal is for a prospective, open-label, randomized controlled trial to determine the effect of preoperative acupuncture on preoperative anxiety and postoperative pain for high-anxiety patients undergoing total hip arthroplasty or total knee arthroplasty. We hypothesize that preoperative acupuncture will reduce preoperative anxiety and postoperative pain as well as reduce postoperative nausea and vomiting and opioid consumption and improve patient satisfaction. The study population is to include adult patients undergoing lower extremity total joint arthroplasty, including of the hip and knee joints, at the Bone-and-Joint Institute at Hartford Hospital.

Table of Contents

OVERVIEW	1
1.0 OBJECTIVES AND SCIENTIFIC AIMS	3
2.0 BACKGROUND AND RATIONALE	3
3.0 OVERVIEW OF STUDY DESIGN/INTERVENTION	5
3.1 Design	5
3.2 Randomization	5
3.3 Acupuncture Intervention	5
3.4 Therapy Materials	6
4.0 CRITERIA FOR SUBJECT ELIGIBILITY	6

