1.0 OBJECTIVES AND SCIENTIFIC AIMS

Primary Objectives: In patients with high anxiety undergoing THA or TKA:

- 1) Determine if preoperative acupuncture reduces preoperative anxiety in the acupuncture group.
- 2) Examine postoperative pain following acupuncture compared to control.

Secondary Objective: To determine the safety of preoperative acupuncture by recording complications throughout hospital length of stay; to determine whether preoperative acupuncture reduces postoperative nausea and vomiting, reduces postoperative opioid consumption, reduces anxiolytics need during hospitalization and improves satisfaction compared to control in high-anxiety patients undergoing THA or TKA.

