7.2 Control Group

1. On the day of surgery and prior to procedure, study patients will be waiting in the preoperative area.
2. The patient will be placed in bay #1 or other bay if #1 is not available in the preoperative area.
3. A member of the study personnel will assess the patient's baseline anxiety and pain.
4. The patient will undergo their surgical procedure.
5. The patient will be reevaluated for pain three times; when they arrive to the post-anesthesia recovery unit (PACU), after an hour, and after three hours.
6. The patient will be reevaluated for PONV/Impact score two times; after an hour from their arrival to the post-anesthesia recovery unit (PACU), and after 3 hours. Postoperative antiemetics used will also be collected from

- the patient's chart retrospectively, following enrollment.
7. Postoperative opioid consumption and anxiolytics used throughout hospitalization will be collected from the patient's chart retrospectively, following enrollment.
 8. Admission and discharge dates & times will be collected directly from the patient's chart retrospectively, following enrollment and used to determine total hospital length of stay.
 9. Patient satisfaction regarding surgery will be evaluated within a week after the discharge from the hospital.

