8.0 OUTCOME EVALUATION

All outcomes will be measured during the time periods illustrated in Table 1 using the following measurement methods:

- PreOP anxiety: Amsterdam Preoperative Anxiety and Information Scale (APAIS; Appendix I)
- State anxiety: Visual Analogue Score (VAS; Appendix VI) will be compared between pre and post acupuncture in the same patient within the acupuncture group.
- State anxiety: Visual Analogue Score (VAS; Appendix VI) preop anxiety assessment will be compared between the two groups to assess their baseline preop anxiety status on day of surgery.
- Pain: 11-point Numeric Pain Rating Scale (NPS; Appendix V) will be compared between the two groups
- Postoperative opioid consumption: collected through EPIC and converted into morphine milligram equivalents (MMEs) using Appendix IV. This will be compared between the two groups. Postoperative nausea and vomiting (PONV): PONV impact score (Appendix VII) will be compared between the two groups. Additionally, postoperative antiemetics needed during hospital admission will be collected directly from EPIC and compared between the two groups.
- Satisfaction with surgery: questionnaire (Appendix III) provided by a member of the study personnel by phone within a week after the discharge from the hospital.
- Adverse events related to the interventions will be recorded throughout enrollment.
- Anxiolytics medication needed throughout hospitalization will be collected directly from EPIC and compared between the two groups.
- Hospital length of stay will be collected directly from EPIC using hospital admission and discharge dates & times; this will be compared between the two groups.

Table 1. Outcome measurement time, researcher-to-patient interface, and method for all study outcomes.

[figure not shown]
Time	Interface	Outcome/ Measurement (Acupuncture)	Outcome/ Measurement (Control)
-10 to -7 days	PREPARE Center	
 • Preoperative anxiety/APAIS 	
 • Preoperative anxiety/APAIS

HHC-IRB
 IRB NUMBER: HHC-2021-0348
 IRB APPROVAL DATE: 06/02/2023

PreAQ/PreOP	Holding bay	
 • Anxiety/VAS • Pain/NPS • Anxiolytics 	
 • Anxiety/VAS • Pain/VAS • Anxiolytics
PostAQ/PreOP	Holding bay	
 • Anxiety/VAS • Pain/NPS 	NA

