10.0 PROTECTION OF HUMAN SUBJECTS

Every effort will be made to ensure the safety of our patients and the confidentiality of their medical information. During the enrollment and consent process, all risks, benefits, side effects, and alternatives will be discussed. Also, it will be stressed that this is a voluntary study and that the patient can withdraw without prejudice at any time.

Benefits

The potential benefit of this study is that preoperative acupuncture is effective in reducing preoperative anxiety and postoperative pain in patients undergoing lower extremity total joint arthroplasty. Such a reduction in postoperative pain and anxiety could potentially increase overall patient satisfaction. Further, patients will not be compensated for participating in this study, but they will receive the acupuncture service at no cost.

Risks

The risks of participation include the risks associated with performing acupuncture include, but are not limited to, the following: minor bleeding, pain, pneumothorax, abdominal injuries, heart injuries, CNS injuries, neck injuries, eye injuries, peripheral nerve injuries, and infection.

Alternatives

The alternative to acupuncture for addressing high-anxiety patients is the standard of care. For pain, this includes the use of standard pain medications, including opioid and non-opioid analgesics, in addition to regional blocks. For anxiety, this includes the regular use of anxiolytic medications and psychological consultation referrals. These standard-of-care procedures will not be replaced by acupuncture and rather performed in adjunct. A patient's decision on whether or not to participate in this study will not affect the availability of standard and supportive measures.

Costs

There will be no additional cost incurred by the participant to participate in the study.

Acupuncture materials and service will be provided at no additional cost to the patients enrolled in the study and will be provided by one of the study investigators.

Voluntary Nature of Study

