For the primary aim *pain*, based on data from the first 31 patients enrolled, our sample size calculation indicates that a minimum of 26 subjects per group are needed using a repeated measures design (each subject is measured 4 times) with 2 groups for a total of 52 subjects. This design achieves 81% power to test factor B1 if a Geisser-Greenhouse Corrected F Test is used with a 5% significance level and the actual effect standard deviation is 0.255 (an effect size of 0.40319). We estimate an attrition rate of 10%, which will require 58 subjects; however we will aim to enroll 60 subjects (30 per group). For the second primary aim *anxiety*, we performed two sample size calculations. One based on the data of all 17 patients in the acupuncture group, and another excluding the 3 patients for which protocol deviations were reported due to methods collecting the anxiety measure. With all 17 patients, the difference in the response of anxiety from pre to post acupuncture was normally distributed with a standard deviation 26.27. If the true difference in the mean response of matched pairs is 35.64, we will need to study 6 pairs of subjects to be able to reject the null hypothesis that this response difference is zero with probability (power) 0.8. The Type I error probability associated with this test of this null hypothesis is 0.05. With the 3 patients removed, the difference in the response of anxiety from pre to post acupuncture was normally distributed with standard deviation 26.588. If the true difference in the mean response of matched pairs is 39.14, we will need to study 6 pairs of subjects to be able to reject the null hypothesis that this response difference is zero with probability (power) 0.8. The Type I error probability associated with this test of this null hypothesis is 0.05.

Pain is the more appropriate primary outcome of the two primary outcomes to base the sample size on because there are 4 time points of data for each group for this variable. The other primary outcome, *anxiety* does not have a post measure for the control group (per the study design), and therefore a within-group pre to post change in the acupuncture group is being performed to examine this outcome. We acknowledge that this within group design is weaker than the design to assess the pain outcome measure.

Statistical Methods

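### The anxiety co-primary is an uncontrolled pre-to-post change in the acupuncture arm, yet the aims are worded as an effect of acupuncture and the analysis section promises a between-group comparison

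*Combined protocol and SAP*

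**What the plan says.** **The aim.** The Overview describes a randomised controlled trial "to determine the effect of preoperative acupuncture on preoperative anxiety and postoperative pain for high-anxiety patients" and hypothesises a reduction in both. Objective 1 in section 1.0 is to "Determine if preoperative acupuncture reduces preoperative anxiety in the acupuncture group". Objective 2 (pain) and the efficacy items in the secondary objective are set against control.

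**The measurement.** Section 8.0 says that the VAS for state anxiety "will be compared between pre and post acupuncture in the same patient within the acupuncture group". Between the arms, only the first VAS is compared: the "preop anxiety assessment will be compared between the two groups to assess their baseline preop anxiety status on day of surgery". For controls, section 7.2 has one rating ("A member of the study personnel will assess the patient's baseline anxiety and pain") and the next step is surgery. Table 1 enters NA for controls at the post-acupuncture, preoperative time point.

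**The analysis.** Under Sample Size, section 11.0 explains that this outcome "does not have a post measure for the control group (per the study design), and therefore a within-group pre to post change" is used for treated patients only, gives a matched-pairs calculation, and concedes that this is weaker than the design for pain. Under Statistical Methods, the same section says that primary and secondary outcomes will be compared between groups. It names no paired test.

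**The concern.** Randomisation contributes nothing to this outcome. The paired test asks whether mean anxiety differs between two ratings in treated patients. It cannot tell acupuncture from anything else that changes between them, such as the passage of time, a practitioner's attention or about 20 minutes of sitting quietly. The plan admits a weaker design but does not say what may be concluded from it.

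At stake is one of two primary objectives. A significant paired test could be reported as showing, within a randomised trial, that acupuncture reduces anxiety. The initial sizing table in section 11.0 used a different quantity, a treatment-versus-no-treatment difference in change scores, which the current design cannot estimate.

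There is also a drafting conflict. The between-group sentence under Statistical Methods fits the baseline VAS but cannot be applied to post-treatment anxiety.

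**Working it through.** **Inputs (section 11.0).** All 17 acupuncture patients at the interim: SD of paired change 26.27, assumed true difference 35.64. With 3 protocol deviations removed (14 patients): SD 26.588, difference 39.14. Two-sided 5% test. Target 30 per group with 10% attrition, so 30 × 0.9 = 27 evaluable. Changes are in the units of section 11.0; a 0–100 scale is inferred, because the VAS appendix is not in the text.

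**1. The plan's own figure.** The plan states 6 pairs at 80% power in both cases.
- 35.64/26.27 = 1.357. Exact noncentral t gives power 0.757 at 6 pairs and 0.847 at 7. An iterated t formula gives 6.4.
- 39.14/26.588 = 1.472. Power is 0.819 at 6 pairs.

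The stated figures reproduce to within one pair, so the arithmetic is not the problem.

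**2. What the paired test calls significant.** The threshold is t(0.975, n−1) × SD/√n.
- n = 27, SD 26.27: 2.056 × 5.056 = 10.4 points.
- n = 24 (if the 3 deviations are among the 27), SD 26.588: 2.069 × 5.427 = 11.2 points.

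No term in this formula depends on the cause of the fall.

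**3. Illustration with assumed falls.** Suppose acupuncture adds nothing and anxiety falls for other reasons. The probability of p < 0.05 is:

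| True fall (assumed) | n = 27, SD 26.27 | n = 24, SD 26.588 |
|---|---|---|
| 0 | 5% | 5% |
| 5 | 16% | 14% |
| 10 | 48% | 42% |
| 15 | 81% | 75% |
| 20 | 97% | 94% |

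No section gives the size of such a fall. If anxiety rises as surgery approaches, the paired test would understate a benefit.

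**4. The interim change.** If 35.64 is the observed mean of the 17, its 95% CI is 35.64 ± 2.120 × 26.27/√17 = 35.64 ± 13.5, or about 22 to 49. For the 14 it is 39.14 ± 15.4, or about 24 to 54. Every assumed fall in step 3 lies below both intervals.

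**5. What a late control rating could detect.** The interim had 31 − 17 = 14 controls. If nobody has enrolled since, 13 acupuncture patients and 16 controls remain to reach 30 each. Assume that controls have the same SD of change.
- Change scores, 80% power: 28.5 points for 13 v 16 (95% CI half-width about 20), and 30.2 for 12 v 14 after 10% attrition.
- ANCOVA, with residual SD = 26.27 × √((1 + r)/2), which assumes equal variances before and after: for r = 0.3, 0.5 and 0.7 the SD is 21.2, 22.8 and 24.2. For 13 v 16 the detectable difference is 23.0, 24.7 and 26.3.
- Allowing for chance baseline imbalance, ANCOVA gives 23.5 to 26.8 for 13 v 16 and 24.9 to 28.5 for 12 v 14.
- At half the interim change (35.64/2 = 17.82), ANCOVA power for 13 v 16, with the same allowance, is 0.57, 0.51 and 0.46.
- If only 8 v 8 remain, about 40 points by change scores.

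**The case against.** **The design is open and deliberate.** Objective 1 is confined to the acupuncture group while objective 2 is set against control. Section 8.0 repeats the within-patient comparison, Table 1 marks the control cell NA, and section 11.0 calls the design weaker and declines to size the trial on it. This stands, and it rules out any suggestion of concealment. But naming who is measured and ranking two designs does not say what may be concluded, and the causal wording remains in the Overview and objective 1.

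**The assumed falls do not match the trial's data.** This also stands. A reader might infer from the 16% to 97% rates that the interim result is probably non-specific. The documents do not support that: a fall of 5 to 20 points would not by itself account for the interim change, so a larger non-specific fall would be needed. The rates show what the test responds to, not how likely a false claim is.

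**Anxiolytics.** Section 10.0 describes standard care that continues alongside acupuncture: "For anxiety, this includes the regular use of anxiolytic medications and psychological consultation referrals". A reader might infer that drugs drive the change. Table 1 lists anxiolytics at the pre-acupuncture time point, not the post-acupuncture one, and no section shows dosing between the two ratings. The possibility is open but not shown. A controlled comparison of drug use is planned ("Anxiolytics medication needed throughout hospitalization will be collected directly from EPIC and compared between the two groups"), but it does not measure objective 1.

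**A late control rating is a weak remedy.** It covers a subset, is added after interim data were seen, and may be infeasible. This is a good reason to put the wording change first.

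**The missing test name is minor.** Agreed: the paired analysis is described elsewhere in section 11.0, and one sentence repairs it.

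**Conclusion.** The concern holds in a limited form and should be fixed. As planned, a significant anxiety result shows that mean VAS anxiety changed in acupuncture patients. It does not show that acupuncture caused the change, and nothing in the plan restricts the conclusion accordingly. An observed mean fall above about 10.4 points suffices with 27 patients (11.2 with 24), given the interim SDs.

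Stronger readings are tempting but unsupported. The paired test does not have an inflated error rate for its own null hypothesis of zero mean change. The documents do not show that the interim fall is an artefact, and a bias could run in either direction. They set no success rule for anxiety beyond the test itself, so a wrongly claimed result is a risk of the wording, not a stated intention. The randomised pain comparison, on which the sample size rests, is unaffected.

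The step 4 intervals assume that 35.64 and 39.14 are observed means. The control-comparison figures assume 29 patients remaining, a control SD equal to that of the acupuncture arm and, for ANCOVA, the stated correlations.

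**What to change.** **1. In all cases.**
- Restate objective 1 and the Overview hypothesis so that the paired VAS change is reported as an uncontrolled within-arm change that supports no efficacy conclusion.
- Name the paired test under Statistical Methods.
- Exempt post-treatment anxiety without a control rating from the between-group sentence, and keep the baseline VAS comparison in section 8.0.

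This costs only a text amendment and needs no new data.

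**2. If enough patients remain.** For patients randomised after the amendment, add a second one-item VAS in controls, in the holding bay before surgery, timed as closely as feasible to the acupuncture arm's post rating. Analyse the second VAS by arm with the first as covariate. Make this the only analysis that can support a between-arm statement on anxiety, worded as acupuncture plus its attention and rest versus no intervention, because the trial is open-label without a sham. Report the 95% CI and state the low precision: about 23 to 30 points detectable at 80% power if 29 patients remain.

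The cost is one extra item in patients whom study staff already assess in the bay. The documents do not say whether controls stay there for a matched interval, so some ratings may be mistimed or missed. Controls already enrolled lack the rating. Current accrual is not stated, and the comparison may not be feasible; the first part then stands alone.

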Patient demographic and clinical (including operative) characteristics will be compared between groups using an independent samples t-test if continuous data are normally distributed), or Mann Whitney U if continuous data are not normally distributed. A chi-square or Fisher's exact test (if cell counts are <5) will be used to compare these characteristics between groups for categorical variables. All continuous variables will be expressed as mean±SD or median, IQR as appropriate. Categorical variables will be expressed as frequency (%).

The primary and secondary study outcomes will be compared between groups two ways. First, an independent samples t-test or Mann Whitney U test if deemed more appropriate for the scale data (which may be considered ordinal) will be used to compare outcomes at each time point between the two groups. Second, a mixed model for repeated measures will be used to compare the study outcomes that are repeated over time (e.g., Pain). This model was chosen instead of a repeated measures ANOVA due to the ordinal nature of the repeated outcome measures in addition to this test being more appropriate for non-normal residuals, missing data, as well as the ability to treat the time points as discrete categories or as true numbers, which accounts for any variability in when the measures are administered to patients.

We anticipate that the timing of the measures being administered may fluctuate slightly due to measures being taken PostOP.

All analyses will be conducted using SPSS version 26.0. P (2-sided) < .05 will be deemed the level of statistical significance.

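### Primary pain has separate tests at each time point and a mixed model, all at 0.05, with no deciding test named; the effect used for sizing also includes a preoperative rating

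*Combined protocol and SAP*

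**What the plan says.** Section 1.0 sets the pain objective as postoperative pain, acupuncture against control. It gives no time point or summary measure.

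Section 11.0 (Statistical Methods) says "The primary and secondary study outcomes will be compared between groups two ways". The first is a t-test or Mann-Whitney U, which "will be used to compare outcomes at each time point between the two groups". The second is the mixed model, with pain as its example. One advantage given for the model is "the ability to treat the time points as discrete categories or as true numbers". The only decision rule is "P (2-sided) < .05 will be deemed the level of statistical significance". No ranking of the analyses, model contrast or adjustment is stated.

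Section 11.0 (Sample Size) re-estimates the number of patients from the first 31 enrolled: 26 per group, each measured four times. It states: "This design achieves 81% power to test factor B1 if a Geisser-Greenhouse Corrected F Test is used with a 5% significance level". It prefers pain to anxiety for sizing because "there are 4 time points of data for each group for this variable".

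Sections 7.1, 7.2 and 8.0 (Table 1) schedule three postoperative pain ratings in both groups: on PACU arrival, at 1 hour and at 3 hours. Controls have one preoperative rating. Acupuncture patients have two, one before and one after the needling.

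**The concern.** Followed as written, the plan produces at least four pain results, each judged at 0.05: three PACU comparisons and a model result. It does not say what happens when they disagree. If one PACU time is significant and the model is not, the plan cannot say whether the primary pain result is positive or negative. The trial is open-label and the team has already used pain data from 31 patients, so this should be settled in writing before the final analysis.

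There is a second gap even if the model decides. The sized group effect averages four ratings, one of them taken before surgery. That is a different quantity from the postoperative pain named in the objective, and the stated power belongs to it.

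**Working it through.** **1. The plan's own figure.** Inputs from Section 11.0 (Sample Size): N = 52, f = 0.40319, alpha 0.05. For a between-group factor with two groups, the degrees of freedom are 1 and 50.

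- Noncentrality = N × f² = 52 × 0.40319² = 8.45
- Critical F(1, 50) = 4.03
- Power = 0.814

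This reproduces the stated 81%, so the sized test is one group effect on the patient's average over four ratings.

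**2. Which four ratings.** Controls have exactly four: one preoperative and three PACU. Acupuncture patients have five: baseline, post-acupuncture and three PACU. Four per group therefore means three PACU ratings plus one preoperative rating. In controls that is the baseline; in the acupuncture group it is either the baseline or the post-acupuncture rating, and the text does not say which.

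**3. False-positive rate for pain.** Simulated trials with no effect: 26 per arm, normal ratings, equal correlation r between times, 200,000 trials per setting. Each PACU time gets a t-test, and the model group effect is a t-test on the patient mean of the three PACU ratings. The documents give no r, so it is assumed.

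| | r = 0.2 | r = 0.5 | r = 0.7 | r = 0.9 |
|---|---|---|---|---|
| Any PACU test or the model | 15.1% | 12.9% | 11.2% | 8.4% |
| A PACU test significant, model not | 10.2% | 8.0% | 6.2% | 3.5% |

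The model alone gives about 5% throughout. Using the four-rating model effect in the first row changes little: 15.6%, 13.3%, 11.4% and 8.5%.

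**4. Does 81% carry over to three PACU ratings?** Let k be the group difference in the fourth rating as a multiple of the four-rating average difference. The mean PACU difference is then (4 − k)/3 times that average. With equal correlation and equal variances:

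f₃ = 0.40319 × √{[(1 + 3r)/4] / [(1 + 2r)/3]} × (4 − k)/3

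Power at N = 52, r from 0.2 to 0.7, no covariate:

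| k | Power |
|---|---|
| 1.5 | 60–65% |
| 1 | 75–80% |
| 0 | 94–96% |
| −1 | above 99% |

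Example, r = 0.5 and k = 1: f₃ = 0.40319 × √(0.625/0.6667) = 0.390, power 79%. The documents give neither k nor r, so these rows only show that the 81% does not transfer.

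**The case against.** The best defence is that the plan already points to the model. Pain is sized on one between-group repeated-measures test, and the methods text explains why a mixed model replaces repeated-measures ANOVA. Nothing says that one significant time point would count as success. This largely stands: it is the more natural reading, and it gives 5%. But a sample-size paragraph is not a decision rule. The methods text lists the per-time-point tests first and does not call them supportive.

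A reader might infer more than the documents support:

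- **That the trial's pain error rate is 11–15%.** This needs both a rule that any significant test counts, which the plan does not state, and an assumed correlation.
- **That the fourth rating must be the pre-treatment baseline in both groups.** The acupuncture group has two preoperative ratings, so it need not be.
- **That power on PACU ratings falls to 75–80%, or rises to 94–96%.** Each is one illustrative case among many.
- **That the two primary outcomes need a joint adjustment.** Section 1.0 lists them as separate objectives, one within-group and one between-group. Separate conclusions do not require one.

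It is also fair that treating time as a number has a stated purpose: measurement times may vary after surgery. The defect is that the choice is left open.

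**Conclusion.** The point holds as an unresolved choice with a bounded consequence. The plan names no deciding pain test or model contrast. The error rate is 5% if one model contrast decides, and about 11–15% if any PACU test or the model may count (assumed correlation 0.7 to 0.2; 8.4% at 0.9). Separately, the sized group effect includes a preoperative rating while the objective is postoperative, so the 81% does not describe power for the stated objective. Its direction of change cannot be determined from the documents. This should be fixed. It is a cheap improvement and does not show that the trial's conclusion will be wrong.

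**What to change.** In Section 11.0:

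1. Name the mixed-model group effect over the three PACU pain ratings as the single confirmatory pain test at two-sided 0.05. Enter the pre-treatment baseline pain rating as a covariate and not as an outcome.
2. State in advance how time is coded. Categories are the simple choice; actual measurement times can be a sensitivity analysis.
3. Report the per-time-point comparisons as supportive estimates with confidence intervals.
4. Disclose that these choices were made after the 31-patient interim look.
5. Recompute power for this contrast from the interim data. Without those data any replacement for the 81% is only illustrative.

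Before using the covariate, reconcile Table 1, which lists preoperative pain as VAS in controls and NPS in the acupuncture group.

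The cost is SAP wording, a disclosure and a restated power figure; no visits or measurements are added. There are two downsides. A difference at one PACU time alone can no longer be claimed as the primary pain result, and the restated power may be below 81%.
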